7.8.1. Update MEDRA 24.1 to MEDRA 25.1

Due to updates to the MEDRA version, the following PTs are added

Cardiac Arrhythmia (Preferred Term)
Atrial standstill
X-ray or Radiologic Pneumonia (Preferred Terms)
Pulmonary blastomycosis
Acute Cerebrovascular Events (Preferred Term)
Vertebrobasilar artery dissection

7.9. Appendix 9 Area Under the Curve Calculation

In the calculation of the AUC, not only the date, but also the timing (the real hours, minutes and seconds as captured in the database should be used, but the AUC result should be reported in hours), of the assessment, is taken into account.

$$\mathbf{AUC\ of\ total\ score} = \sum_{i=2}^T \frac{[TS_{t_i} + TS_{t_{(i-1)}}]}{2} [t_i - t_{(i-1)}] \quad \mathbf{(1)}$$

where

t_i = (actual) timepoint i

t_{i-1} = (actual) timepoint ($i - 1$)

T = last timepoint

t_1 = first timepoint

TS_{t_i} = Total score at (actual) timepoint i

$TS_{t_{(i-1)}}$ = Total score at (actual) timepoint ($i - 1$)

7.10. Appendix 10 Therapeutic Interventions of Interest

Corticosteroid's prescription

ATC codes	ATC Text
A01AC	Corticosteroids for local oral treatment
A07EA	Corticosteroids acting locally
A11ED	Vitamin B-complex with anabolic steroids
A14A	Anabolic steroids
C05AA	Corticosteroids
D01AC	imidazoles/triazoles in combination with corticosteroids (subset of terms with this ATC code)
D07	CORTICOSTEROIDS, DERMATOLOGICAL PREPARATIONS
D07A	CORTICOSTEROIDS, PLAIN
D07AA	Corticosteroids, weak (group I)
D07AB	Corticosteroids, moderately potent (group II)
D07AC	Corticosteroids, potent (group III)
D07AD	Corticosteroids, very potent (group IV)
D07B	CORTICOSTEROIDS, COMBINATIONS WITH ANTISEPTICS
D07BA	Corticosteroids, weak, combinations with antiseptics
D07BB	Corticosteroids, moderately potent, combinations with antiseptics
D07BC	Corticosteroids, potent, combinations with antiseptics
D07BD	Corticosteroids, very potent, combinations with antiseptics
D07C	CORTICOSTEROIDS, COMBINATIONS WITH ANTIBIOTICS
D07CA	Corticosteroids, weak, combinations with antibiotics
D07CB	Corticosteroids, moderately potent, combinations with antibiotics
D07CC	Corticosteroids, potent, combinations with antibiotics
D07CD	Corticosteroids, very potent, combinations with antibiotics
D07X	CORTICOSTEROIDS, OTHER COMBINATIONS
D07XA	Corticosteroids, weak, other combinations
D07XB	Corticosteroids, moderately potent, other combinations
D07XC	Corticosteroids, potent, other combinations
D07XD	Corticosteroids, very potent, other combinations
D10AA	Corticosteroids, combinations for treatment of acne
G01B	ANTIINFECTIVES/ANTISEPTICS IN COMBINATION WITH CORTICOSTEROIDS
G01BA	Antibiotics and corticosteroids
G01BC	Quinoline derivatives and corticosteroids
G01BD	Antiseptics and corticosteroids
G01BE	Sulfonamides and corticosteroids
G01BF	Imidazole derivatives and corticosteroids
H02	CORTICOSTEROIDS FOR SYSTEMIC USE
H02A	CORTICOSTEROIDS FOR SYSTEMIC USE, PLAIN
H02B	CORTICOSTEROIDS FOR SYSTEMIC USE, COMBINATIONS
H02BX	Corticosteroids for systemic use, combinations
M01BA	Antiinflammatory/antirheumatic agents in combination with corticosteroids
N02CB	Corticosteroid derivatives
R01AD	Corticosteroids
R03AK	Adrenergics in combination with corticosteroids or other drugs, excl. anticholinergics
R03AL	Adrenergics in combination with anticholinergics incl. triple combinations with corticosteroids
R03BA	Corticosteroids for inhalation
S01BA	Corticosteroids, plain
S01BB	Corticosteroids and mydriatics in combination
S01CA	Corticosteroids and antiinfectives in combination
S01CB	Corticosteroids/antiinfectives/mydriatics in combination
S02B	CORTICOSTEROIDS
S02BA	Corticosteroids
S02C	CORTICOSTEROIDS AND ANTIINFECTIVES IN COMBINATION
S02CA	Corticosteroids and antiinfectives in combination
S03B	CORTICOSTEROIDS
S03BA	Corticosteroids

ATC codes	ATC Text
S03C	CORTICOSTEROIDS AND ANTIINFECTIVES IN COMBINATION
S03CA	Corticosteroids and antiinfectives in combination
H02AB	Glucocorticoids

Bronchodilator/nebulizer treatment

ATC Code	ATC Text
R03	Drugs for Obstructive Airway Diseases
R03A	Adrenergics Inhalents
R03AA	Alpha-and beta-adrenoreceptor agonists
R03AB	Non Selective beta-adrenoreceptor agonists
R03AC	Selective beta-2-adrenoreceptor agonists
R03AH	Combinations of adrenergics
R03AK	Adrenergics and other drugs for obstructive airway diseases
RO3AL	Adrenergics in combination with corticosteroids or other drugs excl. anticholinergics
R03B	Other Drugs for Obstructive Airways Diseases, Inhalents
R03BA	Glucocorticoids
R03BB	Anticholinergics
R03BC	Antiallergic agents excl. corticosteroids
R03BX	Other Drugs for Obstructive Airways Diseases, Inhalents
R03C	Adrenergics for systemic use
R03CA	Alpha-and beta-adrenoreceptor agonists
R03CB	Non Selective beta-adrenoreceptor agonists
R03CC	Selective beta-2-adrenoreceptor agonists
R03CK	Adrenergics and other drugs for obstructive airway diseases
R03D	Other Systemic Drugs for Obstructive Airways Disease
R03DA	Xanthines
R03DB	Xanthines and Adrenergics
R03DC	Leukotriene receptor agonists
R03DX	Other Systemic Drugs for Obstructive Airways Disease
C01CX	Other cardiac stimulants
R01AX	Other nasal preparations

Antibiotic prescription

ATC Code	ATC Text
A01AB	Antiinfectives and antiseptics for local oral treatment
A02BD	Combinations for eradication of Helicobacter pylori
A07A	Intestinal antiinfectives
C05AB	Antibiotics
D01AA	Antibiotics
D06	Antibiotics and chemotherapeutics for dermatological use
D07C	Corticosteroids, combinations with antibiotics
D09AA	Ointment dressings with antiinfectives
D10AF	Antiinfectives for treatment of acne
G01	Gynecological antiinfectives and antiseptics
J01	Antibacterials for systemic use
J01A	Tetracyclines
J01AA	Tetracyclines
J01B	Amphenicols
J01BA	Amphenicols
J01C	Beta-Lactam Antibacterials, penicillins
J01CA	Penicillins with extended spectrum
J01CE	Beta-lactamase sensitive penicillins
J01CF	Beta-lactamase resistant penicillins
J01CG	Beta-lactamase inhibitors

ATC Code	ATC Text
J01CR	Combinations of penicillins, incl. beta-lactamase inhibitors
J01D	Other Beta-Lactam Antibacterials
J01DB	First generation cephalosporins
J01DC	Second generation cephalosporins
J01DD	Third generation cephalosporins
J01DE	Fourth generation cephalosporins
J01DF	Monobactams
J01DH	Carbapenems
J01DI	Other cephalosporins and penems
J01E	Sulfonamides and Trimethoprim
J01EA	Trimethoprim and derivatives
J01EB	Short acting sulfonamides
J01EC	Intermediate-acting sulfonamides
J01ED	Long-acting sulfonamides
J01EE	Combinations of sulfonamides and trimethoprim, incl derivatives
J01F	Macrolides, Lincosamides and Streptogramins
J01FA	Macrolides
J01FG	Streptogramins
J01G	Aminoglycoside Antibacterials
J01GA	Streptomycins
J01GB	Other aminoglycosides
J01M	Quinolone Antibacterials
J01MA	Fluoroquinolones
J01MB	Other quinolones
J01R	Combinations of antibacterials
J01RA	Combinations of antibacterials
J01X	Other Antibacterials
J01XA	Glycopeptide antibacterials
J01XB	Polymyxins
J01XC	Steroid antibacterials
J01XD	Imidazole derivatives
J01XE	Nitrofurans derivatives
J01XX	Other Antibacterials
J01FF	Lincosamides
J02AA	Antibiotics
J04	Antimycobacterials
J07A	Bacterial vaccines
J07C	Bacterial and viral vaccines, combined
L01D	Cytotoxic antibiotics and related substances
R02AB	Antibiotics
S01A	Antiinfectives
S01AA	Antibiotics
S01AB	Sulfonamides
S02A	Antiinfectives
S02AA	Antiinfectives
S02C	Corticosteroids and antiinfectives in combination
S02CA	Corticosteroids and antiinfectives in combination
S03	Antiinfectives
S03AA	Antiinfectives
S03C	Corticosteroids and antiinfectives in combination
S03CA	Corticosteroids and antiinfectives in combination

Antiviral prescription

ATC Codes	ATC Text
D06BB	Antivirals
J05	Antivirals for systemic use

ATC Codes	ATC Text
J05A	Direct acting anti-virals
J05AA	Thiosemicarbazones
J05AB	Nucleosides and nucoetides exc. Reverse transcriptase inhibitors
J05AC	Cyclic amines
J05AD	Phosphonic acid derivatives
J05AE	Protease inhibitors
J05AF	Nucleosides and nucoetides reverse transcriptase inhibitors
J05AG	Non-nucleoside reverse transcriptase inhibitors
J05AH	Neuraminidase inhibitors
J05AP	Antivirals for treatment of HCV infections
J05AR	Antivirals for treatment of HIV infections
J05AX	Other antivirals
S01AD	Antivirals

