9.4.1.4. Exploratory Endpoints

For the following exploratory endpoints, similar Exact Poisson regression models as for the primary and secondary endpoints will be used and exact 2-sided 95% CIs for VE (1-relative risk rate) will be calculated. For all exploratory endpoints related to influenza-mediated ARI and LRTD only the proportion of participants meeting the respective endpoints will be summarized.

- First occurrence of RT-PCR-confirmed RSV-mediated LRTD during the first year
- First occurrence of RT-PCR-confirmed RSV-mediated ARI during the first year
- First occurrence of RT-PCR-confirmed RSV-mediated LRTD by subtype (RSV A or RSV B)
- First occurrence of RT-PCR-confirmed RSV-mediated ARIs by subtype (RSV A or RSV B)
- First occurrence of complications associated with RT-PCR-confirmed RSV-mediated ARIs RSV-mediated LRTD, influenza-mediated ARIs and hMPV-mediated ARIs
- First occurrence of hospitalizations associated with RT-PCR-confirmed RSV-mediated ARIs RSV-mediated LRTD, influenza-mediated ARIs and hMPV-mediated ARIs

- First occurrence of pneumonia (radiological or X-ray confirmed) associated with RT-PCR-confirmed RSV-mediated ARIs RSV-mediated LRTD, influenza-mediated ARIs and hMPV-mediated ARIs
- First occurrence of emerging therapeutic interventions of interest associated with RT-PCR-confirmed RSV ARIs. The following are considered emerging therapeutic interventions of interest:
 - New onset or increased dose (compared to baseline) of bronchodilator/nebulizer treatment
 - New onset or increased dose (compared to baseline) of corticosteroid prescription
 - New onset or increased dose (compared to baseline) of antibiotic prescription
 - New onset or increased dose (compared to baseline) of antiviral prescription
- First occurrence of RT-PCR-confirmed hMPV-mediated ARI
- First occurrence of RT-PCR-confirmed hMPV-mediated LRTD

Unless specifically mentioned otherwise, the Ves will be calculated for the above endpoints occurring during the first year, and during the second year and over the whole study. The follow-up time is determined in a similar way as for the primary and secondary endpoints.

If the primary analysis occurs before the end of the study, the secondary endpoints #2, #3 (provided second year data are already available) and #4 might be analyzed descriptively at the time of the primary analysis, VE with 95% CI will be calculated.

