- First occurrence of pneumonia (radiological or X-ray confirmed, as assessed in the CRF diagnostic tests form or reported as a complication) associated with RT-PCR-confirmed RSV-mediated ARIs, RSV-mediated LRTD, influenza-mediated ARIs and hMPV-mediated ARIs
- First occurrence of emerging therapeutic interventions of interest associated with RT-PCR-confirmed RSV-mediated ARIs, RSV-mediated LRTD, influenza-mediated ARIs and hMPV-mediated ARIs. The following are considered emerging therapeutic interventions of interest (Section 7.10) :
 - New onset or increased dose (compared to baseline) of bronchodilator/nebulizer treatment

- New onset or increased dose (compared to baseline) of corticosteroid prescription
- New onset or increased dose (compared to baseline) of antibiotic prescription
- New onset or increased dose (compared to baseline) of antiviral prescription

Note: These will be taken from the concomitant medication pages of the eCRF. The concomitant medications listed in Section 7.10 are considered as therapeutic interventions of interest. The principal investigator will indicate whether there has been new onset of increase in dose compared to baseline in the CRF. Those associated with an ARI or complication of an ARI will be displayed.

- First occurrence of RT-PCR confirmed hMPV-mediated ARI
- First occurrence of RT-PCR-confirmed hMPV-mediated LRTD
- First occurrence of RT-PCR confirmed influenza-mediated ARI and influenza-mediated LRTD
- First occurrence of an RT-PCR-confirmed RSV LRTD assessed as at least mild, as at least moderate and as severe by the CEC during the considered year:
 - with onset at least 14 days after dosing of study vaccine and prior to study Day 365 (first year comparison)
 - with onset from the study Day 365 onwards (second year comparison)
 - with onset at least 14 days after dosing of study vaccine (whole study comparison)

Note: Occurrence is always referring to the time to the start of the ARI as reported in the CRF (CESTDTC). The start of the associated ARI will also be used for calculating the time to first occurrence of emerging therapeutic interventions, pneumonia, complications and hospitalizations.

- First occurrence of RT-PCR-confirmed, RSV-mediated LRTD during the second year and over the whole study (if the primary analysis is conducted before the end of the study):
 - with onset from the study Day 365 visit onwards (second year comparison)

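### SAP Appendix 10 puts drug classes from outside the category into three of the protocol's four treatment categories, so the exploratory therapeutic-intervention endpoint can over-count

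*SAP*

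**What the plan says.** Protocol 9.4.1.4 names four kinds of emerging therapeutic intervention. The first is "New onset or increased dose (compared to baseline) of bronchodilator/nebulizer treatment"; the others are worded the same way for corticosteroid, antibiotic and antiviral prescriptions. SAP 6.5 repeats the four and then makes the code list operative: "The concomitant medications listed in Section 7.10 are considered as therapeutic interventions of interest". Two further conditions apply. The investigator must flag the drug as new or increased against baseline, and it must be associated with the ARI or a complication of it.

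SAP 7.10 gives one ATC table per category. Rows of interest:

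- Corticosteroid: A11ED, "Vitamin B-complex with anabolic steroids"; A14A, anabolic steroids; R03AL, "Adrenergics in combination with anticholinergics incl. triple combinations with corticosteroids"; and R03AK, an adrenergic paired with a corticosteroid or with some other drug that is not an anticholinergic.
- Bronchodilator/nebulizer: R01AX, "Other nasal preparations"; C01CX, cardiac stimulants; and a row printed RO3AL (letter O for zero), labelled "Adrenergics in combination with corticosteroids or other drugs excl. anticholinergics".
- Antibiotic: J07A, "Bacterial vaccines"; and J07C, combined bacterial and viral vaccines.

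Only D01AC, in the corticosteroid table, carries a note limiting it to a subset of the terms under its code.

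**The concern.** A code list that implements a protocol category should hold drugs of that category. Six codes do not fit on the face of their labels, and two more fit only in part. The two extra conditions in SAP 6.5 ask whether the drug is new or increased and whether it is tied to the ARI. Neither asks whether it belongs to the category.

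The outputs at stake are the VE for first emerging therapeutic intervention (SAP 6.5 and 6.5.1), the proportions by subcategory, and the by-subcategory summary at the day of vaccination (SAP 6.5.1). SAP 7.5 also gives special attention to new medications outside the interventions of interest, and any drug wrongly listed in Appendix 10 disappears from that summary.

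**Working it through.** No sample size, power or alpha figure is involved. The check sets each label against its category and then follows the counting rule.

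**Rows.** Counting the four tables in SAP 7.10:

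| Table | Rows | Off-category by label | Share of rows |
|---|---|---|---|
| Corticosteroid | 57 | A11ED, A14A | 2/57 = 3.5% |
| Bronchodilator/nebulizer | 25 | C01CX, R01AX | 2/25 = 8.0% |
| Antibiotic | 71 | J07A, J07C | 2/71 = 2.8% |
| Antiviral | 15 | none | 0/15 = 0% |
| All | 168 | 6 | 6/168 = 3.6% |

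Adding R03AK and R03AL in the corticosteroid table, which are in-category only in part, gives 8/168 = 4.8%. These are shares of codes, not of prescriptions.

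**Which off-category codes can produce events.** A drug must be started or increased for the ARI. Vaccines, anabolic steroids and cardiac stimulants will seldom meet that. Nasal preparations will: nasal congestion is one of the six symptoms that qualify an ARI (Protocol 8.2.2 and Appendix 5), and medications associated with RSV ARIs are recorded for all participants for the whole study (Protocol 6.8). A nasal product begun for RSV congestion meets both conditions and is filed through R01AX as bronchodilator/nebulizer.

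**Effect on the VE.** The endpoint is first occurrence of any listed intervention, timed at the start of the associated ARI. Within one ARI, an off-category drug changes the event count only if the participant has no in-category drug for that ARI. So the VE moves only through participants whose sole listed drug is off-category.

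**R03AL and R03AK.** A steroid-free product under either code is still an airway drug within the bronchodilator table, where the parent R03 is listed. Counting it as corticosteroid therefore leaves the overall VE alone but misstates the corticosteroid subcategory.

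**R03AL labels.** The corticosteroid table's label for R03AL includes anticholinergics; the bronchodilator table's label excludes them. The second closely matches the text given to R03AK in the corticosteroid table, which points to a transcription slip. The two rows still have to be reconciled.

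**Day-of-vaccination summary.** It is taken before any ARI, so the ARI link cannot filter it. A chronic user of a nasal preparation, if recorded, counts as a bronchodilator/nebulizer user at baseline.

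**The case against.** The strongest reply is that this hardly matters. The intended classes are all present (R03, H02, J01, J05), the antiviral table is clean, and the two conditions in SAP 6.5 screen out most of the odd rows in practice. The endpoint is exploratory and outside the testing strategy. SAP 6.11 does not name it among the endpoints of the reduced final analysis. All of that stands. It limits the consequence, but it does not put a nasal preparation into the bronchodilator category.

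A second reply is that C01CX or R01AX may have been included to catch particular drugs. SAP Table 1 records that version 3.0 added three ATC terms to this appendix without saying which or why. The documents cannot settle this, so restricting the two codes to named terms is as acceptable as removing them.

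A reader might go further and infer errors that the documents do not show:

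- L01D, "Cytotoxic antibiotics and related substances", carries the word antibiotics in its own label, and Protocol 6.8 prohibits cancer chemotherapy throughout the study.
- A01AB covers antiinfectives as well as antiseptics for local oral use, so it is not plainly outside the antibiotic table.
- R03BA (inhaled glucocorticoids) is not plainly outside a category that includes nebulizer treatment. Striking its row would also change nothing while R03 and R03B remain listed.
- Drugs that appear in two tables are not an error. Nothing makes the subcategories mutually exclusive, and the overall VE counts each participant once.
- The silence of SAP 7.2 is not an unlogged change. The SAP keeps the protocol's four categories, and Protocol 9.4.1.4 leaves further detail on exploratory endpoints to the SAP.

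**Conclusion.** Appendix 10 over-includes in three of the four categories: six codes are off-category by their labels, and R03AL and R03AK are counted whole as corticosteroid although only part of each is. The practical weight falls on R01AX, in the VE and subcategory tables and in the day-of-vaccination summary.

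A reader might infer that the endpoint fails to measure the four protocol categories. That is too strong: the right classes are listed, and the fault is added events at the margin. A reader might also want a figure for the bias in VE. That would need the share of participants whose only listed drug is off-category, and the VE against such episodes. The documents give neither, so the size cannot be computed. Even the direction rests on an assumption: VE would fall only if the added episodes are ones the vaccine prevents less well.

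Primary and confirmatory secondary inference is untouched, and so is the reduced final analysis in SAP 6.11. The conclusion rests on reading each ATC row by its printed label and on the absence of any subset note on these rows.

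**What to change.** In SAP 7.10:

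1. Remove A11ED and A14A from the corticosteroid table and J07A and J07C from the antibiotic table.
2. Remove C01CX and R01AX from the bronchodilator/nebulizer table, or restrict them to named in-category drug terms, as was done for D01AC, and give the reason.
3. Count R03AL and R03AK as corticosteroid only when the coded product contains a corticosteroid.
4. Correct the RO3AL code and label in the bronchodilator table so that it agrees with the R03AL row in the corticosteroid table.
5. Rerun any therapeutic-intervention VE and subcategory tables that are reported.

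The cost is a code-list edit, a product-level check for two codes, and a rerun. The downside is slightly fewer counted events.

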7.11. Appendix 11 Binomial Exact Test

$$\begin{aligned}
 \text{Vaccine Efficacy} &= 1 - \text{Relative Risk} = 1 - \frac{\frac{\# \text{ of Events}_{VX} / \# \text{ of Subjects}_{VX}}{\# \text{ of Events}_P / \# \text{ of Subjects}_P}}{\# \text{ of Events}_T / \# \text{ of Subjects}_T} \\
 &= 1 - \frac{1}{r} * \frac{\# \text{ of Events}_{VX}}{\# \text{ of Events}_P} = 1 - \frac{1}{r} * \frac{\# \text{ of Events}_{VX} / \# \text{ of Events}_T}{(\# \text{ of Events}_T - \# \text{ of Events}_{VX}) / \# \text{ of Events}_T} \\
 &= 1 - \frac{1}{r} * \frac{\# \text{ of Events}_{VX} / \# \text{ of Events}_T}{1 - \# \text{ of Events}_{VX} / \# \text{ of Events}_T} = 1 - \frac{p}{r * (1 - p)}
 \end{aligned}$$

Where,

$$r = \frac{\# \text{ of Subjects}_{VX}}{\# \text{ of Subjects}_P}$$

$$p = \# \text{ of Events}_{VX} / \# \text{ of Events}_T$$

of Events_{VX} = number of events in the active group

of Events_P = number of events in the Placebo group

of Events_T = number of events, regardless the group

Therefore, there is a monotonic link between VE, the vaccine efficacy, and p, the proportion of subjects in the vaccine group among the total cases in the two groups.

Note that, conditional on the total number of events, **# of Events_{VX}** is binomially distributed (**# of Events_{VX}, n**) with n the expected proportion of events in the vaccine group under the true vaccine efficacy.

The CI for vaccine efficacy can then be derived from the exact CI from p (Dragalin, Fedorov and Chevart, 2002)⁰.

7.13. Appendix 13 Chronic Kidney Disease [CKD] + Diabetes Terms

Chronic Kidney Disease
Artificial kidney device user
Chronic kidney disease
Chronic kidney disease-mineral and bone disorder
Diabetic end stage renal disease
Dialysis
Dialysis device insertion
End stage renal disease
Glomerulonephritis chronic
Haemodialysis
Haemofiltration
Hepatorenal failure
Hyperparathyroidism secondary
Kidney fibrosis
Metabolic nephropathy
Nephrogenic systemic fibrosis
Nephrosclerosis
Oedema due to renal disease
Peritoneal dialysis
Renal and liver transplant
Renal and pancreas transplant
Renal failure
Renal replacement therapy
Renal rickets
Renal transplant
Acquired cystic kidney disease
Acquired hypocalciuric hypercalcaemia
Acquired perforating dermatosis
Acute phosphate nephropathy
Albuminuria
Autoimmune nephritis
C1q nephropathy
C3 glomerulopathy
Chronic allograft nephropathy
Diabetic nephropathy
Dialysis amyloidosis
Dialysis disequilibrium syndrome
Dialysis hypotension
Dialysis induced hypertension
Dialysis membrane reaction
Dialysis related complication
Diffuse mesangial sclerosis
Extensive interdialytic weight gain
Fibrillary glomerulonephritis
Focal segmental glomerulosclerosis
Glomerular filtration rate abnormal
Glomerular filtration rate decreased
Glomerulonephritis
Glomerulonephritis membranoproliferative
Glomerulonephritis membranous
Glomerulonephritis minimal lesion
Glomerulonephritis proliferative
Glomerulonephritis rapidly progressive
Glomerulonephropathy
Glomerulosclerosis
Goodpasture's syndrome
Haemodialysis complication
Haemolytic uraemic syndrome
Hepatitis virus-associated nephropathy

Chronic Kidney Disease
HIV associated nephropathy
Hypercalcaemic nephropathy
Hypertensive nephropathy
IgA nephropathy
IgM nephropathy
Immune-mediated nephritis
Immune-mediated renal disorder
Immunotactoid glomerulonephritis
Inadequate haemodialysis
Inadequate peritoneal dialysis
Intercapillary glomerulosclerosis
Intradialytic parenteral nutrition
Inulin renal clearance decreased
Ischaemic nephropathy
Kidney small
Lupus nephritis
Membranous-like glomerulopathy with masked IgG-kappa deposits
Mesangioproliferative glomerulonephritis
Metabolic acidosis
Microalbuminuria
Nephritic syndrome
Nephropathy
Nephropathy toxic
Nephrotic syndrome
Neutrophil gelatinase-associated lipocalin increased
Obstructive nephropathy
Paraneoplastic glomerulonephritis
Paraneoplastic nephrotic syndrome
Peritoneal dialysate leakage
Peritoneal dialysis complication
Pigment nephropathy
Polyomavirus-associated nephropathy
Potassium wasting nephropathy
Protein urine present
Proteinuria
Red blood cells urine positive
Reflux nephropathy
Renal amyloidosis
Renal atrophy
Renal papillary necrosis
Renal tubular atrophy
Sickle cell nephropathy
Tubulointerstitial nephritis
Ultrafiltration failure
Urate nephropathy
Urea renal clearance decreased
Urine albumin/creatinine ratio abnormal
Urine albumin/creatinine ratio increased
Urine protein/creatinine ratio abnormal
Urine protein/creatinine ratio increased

Diabetes
Acquired lipotrophic diabetes
Diabetes complicating pregnancy
Diabetes mellitus
Diabetes mellitus inadequate control
Diabetes with hyperosmolarity
Diabetic arteritis
Diabetic coma
Diabetic coronary microangiopathy

Diabetes
Diabetic hepatopathy
Diabetic hyperglycaemic coma
Diabetic hyperosmolar coma
Diabetic ketoacidosis
Diabetic ketoacidotic hyperglycaemic coma
Diabetic ketosis
Diabetic metabolic decompensation
Diabetic wound
Euglycaemic diabetic ketoacidosis
Fructosamine increased
Fulminant type 1 diabetes mellitus
Gestational diabetes
Glycosuria
Glycosylated haemoglobin abnormal
Glycosylated haemoglobin increased
Hyperglycaemic hyperosmolar nonketotic syndrome
Hyperglycaemic seizure
Hyperglycaemic unconsciousness
Insulin resistance
Insulin resistant diabetes
Insulin-requiring type 2 diabetes mellitus
Ketosis-prone diabetes mellitus
Latent autoimmune diabetes in adults
Monogenic diabetes
Neonatal diabetes mellitus
New onset diabetes after transplantation
Pancreatogenous diabetes
Steroid diabetes
Type 1 diabetes mellitus
Type 2 diabetes mellitus
Type 3 diabetes mellitus
Anti-GAD antibody positive
Anti-IA2 antibody positive
Anti-insulin antibody increased
Anti-insulin antibody positive
Anti-insulin receptor antibody increased
Anti-insulin receptor antibody positive
Anti-islet cell antibody positive
Anti-zinc transporter 8 antibody positive
Blood insulin abnormal
Blood insulin decreased
Hypoinsulinaemia
Impaired insulin secretion
Increased insulin requirement
Insulin autoimmune syndrome
Insulin therapy
Insulin tolerance test abnormal
Metabolic syndrome
Wolfram syndrome

